## Measures

### Survey

Table 1		How measured	Subj ect	Baselin e	6 Months	12 months	24 months
Measure	Source of Data						
Age	EHR/ Survey*	Years	CG, Pt	X			
Gender	EHR/ Survey	Categorical: Male/Female	CG, Pt	X			
Race/Ethnicity	EHR/ Survey	Categorical: White, Black, Hispanic, other	CG, Pt	X			

Education	Survey	Categorical: < H.S., H.S., Some College, College graduate+	CG	X			X
Clinical co-morbid conditions	EHR	Charlson comorbidity index 	Pt	X	X	X	X
Medication Complexity	EHR	Unique medications (n) + unique multiple administrations/day (n)	Pt	X	X	X	X
Prior (1-year) non-acute use	ResDAC	Counts: physician ambulatory visits	Pt	X	X	X	X
Prior (1-year) acute use	ResDAC	Counts: ED, hospital visits / bed days	Pt	X	X	X	X
Social Support	Survey	MOS Abbreviated Social Support (4-item; 5-point Likert scale) 	CG	X	X	X	X
COVID-19	Survey	Exposure and symptoms, testing status, impact, changes in burden, access to resources	CG, Pt	X			
Follow-up COVID-19	Survey	Exposure and symptoms, testing status, impact, changes in burden, access to resources	CG, Pt		X	X	X
DM-ADRD-Specific							
Dementia Diagnosis /Type	EMR	Categorical: Yes/No and if yes, AD, Lewy Body disease, Parkinson's Disease, Vascular, Frontotemporal, and mixed	Pt	X			X
Dementia Severity	Survey	Dementia Severity Rating Scale 	Pt	X			X
Caregiver relationship to CR	Survey	Categorical: Spouse, child, other relative, friend/other	CG, Pt	X			

Functional State	Survey	14 items: ADL/ IADL for CG; within DSS for Pt	CG, Pt	X	X	X	X
Marital Status	Survey	Categorical: Single/never married, married, divorced, widowed	CG, Pt	X			X
Substance use history	Survey	Current: Yes/No; Past history: Yes/No	CG, Pt	X	X	X	X
Mental illness history	Survey	Yes/No: Depression, schizophrenia, PTSD, other	CG, Pt	X			
Diabetes care questions	Survey	diet, blood sugar testing, exercise	Pt	X	X	X	X
Hypoglycemia	Survey	Number, number documented, treatment, number seek medical attention	Pt				
Neuropathic pain	Survey	Yes/no	Pt	X	X	X	X
Urinary symptoms	Survey	Counts: frequency, dysuria, incontinence, urgency	Pt	X	X	X	X
Falls	Survey	Number, number injurious in last year and then since last survey, number ED or other falls requiring medical attention	Pt	X	X	X	X
Syncope	EHR	Number, number ED diagnoses or other events requiring medical attention	Pt	X	X	X	X
Structural Measures							
General							
Change in PCP-past 6 mo./last survey	EHR	Yes/No	Pt	X	X	X	X
Consistent PCP care	EHR	% Visits by PCP versus other ambulatory providers	Pt	X	X	X	X

New home health aide or increased hours	Survey	Yes/no; HHA resource changes	Pt	X	X	X	X
New home health care services	Survey	Yes/no	Pt	X	X	X	X
Insurance	EHR	Categorical: Yes/No, Medicare, Medicaid, HMO	Pt	X	X	X	X
DM-ADRD-Specific							
Has a caregiver (Defined: Sec. B5)	EHR	Yes/No	Pt	X	X	X	X
Caregiver living arrangement	Survey	Categorical: Live with subject, close proximity (miles), other	CG	X	X	X	X
Clinic-Specific							
Clinic Size	Admin	Number primary care providers / number of patients	Clinic	X			X
Clinic Support	Admin	Number of clinic support staff / provider	Clinic	X			X
Proportion Medicare/Medicaid	Admin	Insurance data specific to Medicare/Medicaid categories	Clinic	X			X
EQUIPED Process of Care Measures							
Provider use of structured template	EHR	Counts: visit note/templates; proportion of visits with templates	PCP		X	X	X

Provider educational attendance	Admin	Proportion (n, %) of educational sessions attended	PCP		X		
PM – PCP Communication	EHR	Counts: emails, forwarded notes between PM and PCP	PM/PCP		X	X	X
Change in diabetic medication	EHR	Counts: change (add, delete); dosing (increase, decrease)	Pt	X	X	X	X
Change in antihypertensive medication	EHR	Counts: change (add, delete); dosing (increase, decrease)	Pt	X	X	X	X
Medication complexity	EHR	Sum of unique medications, daily dosing frequency/differences	Pt	X	X	X	X
Anticholinergic medication burden	EHR	Anticholinergic medication burden scale	Pt	X	X	X	X
PM – CG contact frequency	EHR	Counts: CG visits with PM (by type: email, phone, in-person)	CG		X	X	X
Referrals for CG-support services	EHR	Proportion (n, %) of CGs referred to programs / receipt of service	CG		X	X	X
Cognitive screening of eligible patients	EHR	Proportion (n, %) of DM-eligible patients screened w/ MiniCog TM39	Pt		X	X	X
Outcome Measures							
General							
Hemoglobin A1C Change	EHR	Proportional change: patients with in-range values versus not	Pt	X	X	X	X

Blood pressure change	EHR	Proportional change: patients with in-range values versus not	Pt	X	X	X	X
Treatment Burden Questionnaire	Survey	15-item survey modified for CG administration (0-10 likert) 	Pt	X	X	X	X
Non-acute care use	ResDAC	Counts: provider ambulatory visits / all health system contacts	Pt	X	X	X	X
Acute care use**	ResDAC	Counts: ED, hospital / #bed days	Pt	X	X	X	X
Sub-acute care use	ResDAC	Counts: # bed days	Pt	X	X	X	X
LTC use	ResDAC	Counts: # bed days	Pt				
LTAC or Hospice use	ResDAC	Counts: # bed days	Pt				
DM-ADRD-Specific							
Dementia symptoms	Survey	DSS	Pt /CG	X	X	X	X
Diabetes caregiver distress	Survey	Diabetes Caregiver Distress Scale	CG	X	X	X	X

**LEGEND:** CG=Caregiver; Pt=Patient; EHR=Electronic Health Record; ResDAC=Research Data Assistance Center; DM=Diabetes mellitus; ADRD=Alzheimer's disease and related dementias; ADL=Activities of Daily Living; IADL=Instrumental Activities of Daily Living; HABC-M=Health Aging Brain Care-Monitor; PTSD=Post-traumatic Stress Disorder; ED=Emergency Department; PCP=Primary Care Provider; PM=Panel Manager; MYLOH=Managing Your Loved One's Health; MOS=Medical Outcomes Study TBQ= Treatment Burden Questionnaire,\* Note – the survey is always given to the caregiver (CG)

*and includes questions about the CG and about the patient; \*\* Baseline utilization variables will have 20 month look-back through claims and EHR*

As shown in Table 1, many variables for the evaluation will be collected from the EHR or from claims. However, many caregiver-reported variables will also be collected using scales that have been validated for patients, but usually not for caregivers noting that some have been widely used to investigate how a caregiver perceives the patient's conditions. Below we discuss instruments used for caregiver reported variables, as well as the use of EHR and claims to measure patient-related variables. (Table 1 does not reflect the qualitative evaluation. The qualitative study as discussed in Section 3 and elsewhere above, will investigate the experiences of caregivers, patients and providers.)

Variables describing the patients, caregivers and clinics include: a) characteristics of patients and of caregivers, including demographics, marital status, living arrangements, and general health and function; b) patient medical and utilization characteristics, including comorbid conditions, medication complexity, patient symptoms potentially related to diabetes or to medication use and changes, depression and history of substance uses and healthcare utilization in the prior year. Dementia specific characteristics of the patients include type of dementia, its severity, and function. The survey respondent is always the caregiver, although the questions may measure patient or caregiver status.

We will also measure structure of care variables. These include patient use of consistent PCP care, home health services, and patient insurance. Clinic characteristics are size, support staff number, proportion of Medicare and Medicaid patients. Several baseline variables relate to diabetes but because they are also outcome variables they will be described later. As shown in table 1, many of these baseline and control variables are measured in the EHR and Epic administrative reports, or by claims. Some are measured by validated survey instruments, which are discussed briefly below.

We will collect many process of care measures at baseline and at follow-up. These include: a) provider use of Epic templates and tools; b) provider attendance at educational sessions; c) PM-PCP communication; d) PM-caregiver contact frequency; e) referral for caregiver-support services; f) cognitive screening of diabetes patients over 75; g) change in diabetes medications; h) change in hypertensive medications; i) change in anticholinergic burden; j) change in medication complexity. These variables are measured by EHR review and Epic administrative systems.

Outcome variables include HbA1c level and blood pressure. These variables will be measured at 0, 6, 12 and 24 months when available. Our main outcome is the proportion of patients achieving consensus HbA1c targets. BP will be measured by proportion of patients achieving consensus BP targets per our guideline. These variables will be measured by the EHR.

Utilization outcome variables are ED, hospital, SNF and ambulatory clinic utilization measured by EHR and by claims (for non-New York Langone Health utilization). SNF days must be measured by claims; Epic reports have discharge destination but do not have SNF days. Utilization variables will be measured at 6, 12, 24 months; the baseline measures include a 20 month look back at utilization.

Multiple caregiver reported outcomes about the caregiver and about the patients will also be

collected at 0, 6, 12, 24 months. General outcomes include: a) caregiver perception of care quality (our main caregiver-reported outcome), dyad care goals, preferences, and satisfaction; b) treatment burden; c) caregiver global health. Dementia and diabetes specific outcomes include: a) patient dementia symptoms; b) caregiver diabetes stress.

Below is a brief description of the instruments we will use, all of which have been studied and validated, although not always with caregivers.

- **Social Support MOS-5.** This survey instrument has been used to investigate social support for caregivers of dementia patients and is well studied. It has 5 questions.
- **Global Health (Promis Scale v1.2):** This commonly used instrument from the Promis series of instruments assesses the general health of the caregiver and is reported by the caregivers. It has 10 questions.
- **Diabetes Caregiver Distress Scale:** This scale is adapted from the diabetes distress scale. We were unable to find a diabetes care distress or care burden scale that is directed at caregivers, even when checking literature for type 1 diabetes and children with diabetes. We therefore will use this instrument for caregivers although it is usually given to patients. It has 7 questions.
- **Mental Health and Substance Use:** These 5 questions ask about caregiver history of mental health, including stress and depression, alcohol and illicit drug use.
- **Treatment Burden Questionnaire (TBQ):** This instrument has been used in studies with patients but not with caregivers who are supervising or providing care for care-patients (patients). The form has 15 questions. In order to publish our findings, we are working with experts to conduct psychometric evaluation to validate the TBQ for use with caregivers.
- **Dementia Severity Rating Scale (DSRS):** This is a caregiver questionnaire that asks about the patient's dementia characteristics. It has been used in many studies, including studies by our group, and is well validated. This scale includes questions related to the patient's functional ability.
- **COVID Questionnaire:** This instrument assesses the impact of COVID-19 pandemic and its associated mitigation efforts on study subjects. Specifically, it includes COVID-19 status, related symptoms, and the social, medical and functional impact of the pandemic on caregivers and care recipients. We will attempt to complete this instrument at least once (baseline or follow-up) with every caregiver/care recipient dyad.
- **Follow-up COVID Questionnaire:** This survey will capture any changes that may have occurred since the first COVID survey and will be administered to any participant that has already completed an initial survey.

Most variables measured by EHR and claims are self-explanatory. However, two other instruments will be used with EHR and claims.

- **Patient: Charlson Comorbidity Index:** This well-known modified index will be calculated from the EHR and/or claims.
- **Patient: Anticholinergic Cognitive Burden Scale:** This is also a commonly used scale derived from chart review that has been used in the past by our group.

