### 1.2 Specific Aims

Specific Aims of the R33 Enhanced Quality In Primary Care for Elders with Diabetes-ADRD (EQUIPED-ADRD) are:

- 1) Implement and evaluate a pragmatic trial in a large healthcare system using cluster randomization, and the practice change framework, that will: manage people with co-occurring DM and ADRD according to the guidelines developed to test our hypotheses and identify additional patients with cognitive impairment and inappropriate DM management.
- 2) Test whether EQUIPED-ADRD will increase the proportion of intervention patients who are in desirable glycemic and blood pressure ranges compared to control patients.
- 3) Test whether the EQUIPED-ADRD intervention will improve dyad perception of care quality and reduce treatment burden.
- 4) Test whether dementia symptoms will deteriorate less in intervention subjects compared to controls.

**Exploratory Aim.** Test whether intervention subjects will use fewer health care services than controls and will have less cognitive decline associated with desired changes in glycemic and blood pressure control.

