### **For both the INT and CON clinics:**

We will provide decisional guidance (the guideline); materials about community and NYU Langone Health resources for managing patients with DM-ADRD, particularly caregiver support services; advice on referrals for both DM and cognitive specialty care; provider education, and basic feedback. We will try to identify a clinical champion in all INT and CON clinics.

We will receive some workflow support for the quality improvement program. This will include Epic-based EHR enhancements such as guidance for MiniCog™ cognitive screening; provider scripts for decisional guidance discussions, especially for care de-escalation and cognitive screening results. Basic feedback and education will occur in both INT and CON clinics including yearly meetings with PCPs for education and feedback on DM and ADRD management.

Preparation for the PCPs will occur either before or very soon after the quality improvement program begins. The research team will meet with clinic providers and staff at a monthly meeting. PCPs will receive a 30-60 minutes in person training including introduction to the

decisional guidance, introduction to clinical resources and possibly other educational materials, such as templates and scripts.

Based on the guideline, providers will be encouraged to develop individualized management targets, particularly for HbA1c and BP, for each patient, and re-evaluate these targets over time. Providers will also be trained in cognitive screening with the MiniCog™. Clinic staff will be trained in minor workflow changes related to the intervention.

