### **INT Clinics:**

In the INT clinics we will introduce the panel manager (PM) to all clinic staff and develop processes for interaction. The PM will work with INT clinic providers to individualize communication methods between the PCP and PM. Each month INT clinic providers will get a list of eligible patients who have appointments with them in the coming month - those with diagnoses of DM-ADRD and those 75 and older with DM who are out of range for HbA1c or BP. This process gives providers monthly reminders about the ongoing quality improvement study and is a more intensive form of QI intervention than provided to CON clinics.

Because this is a pragmatic trial, the clinical team and a project-funded PM will deliver the intervention, fitting it as closely as possible into usual clinical workflow. The clinical team includes PCPs, occasional APNs and PAs (who function as PCPs), RN's, MA's, office staff, and clinic onsite administration. The PM will be part of the team; PMs providing chronic disease self-management support (usually telephonic) are clinic team members in many healthcare systems.

We will assign two PMs to 9 randomly selected INT clinics. Each PM will have 4.5 INT clinics and will engage and focus on their first clinics in a randomly ordered step-wise fashion working within 1-2 clinics over a focused 3-month period before moving on to the next 1-2 clinics for 3 months, then the last 1-2 clinics for 3 months. Our preliminary data suggests 20-50 patients per INT clinic with DM-ADRD  $\geq 65$  years; and about an equal number with DM without ADRD who will screen positive for cognitive impairment, most of whom are  $\geq 75$  years and identified by HbA1c/BP over or under treatment, or identified by provider referral, which we will allow. With 9 INT clinics, given our preliminary data about patient numbers, each PM will have an anticipated 300 dyads. PMs can engage about 33 patients/month, making initial 300 patient/CG contact in 9 months.

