We will train intervention PMs in DM and ADRD management for INT clinics. Training will include one-on-one sessions with the mPI's and co-I's, suggested reading, shadowing relevant clinicians, such as social workers in the Alzheimer's Disease Center and geriatrics clinic, and other relevant activities. We expect training will require one month's duration with subsequent continuous learning activities that include continuing meetings with mPIs and co-I's and travel to national conferences.

**PM Activities.** The PM will reach out to eligible patients with diagnosed DM-ADRD (see section 4.3) and  $\geq 75$  year-old patients with over- and under-treatment of HbA1c/BP for cognitive screening using IQ-CODE as defined in the Guideline. For those with a positive screen, in coordination with the PCP, the PM will facilitate further cognitive evaluation. These patients will become part of the quality improvement intervention. The PM will begin telephonic assessment and DM management education of DM-ADRD patients around the time of the scheduled visit (either just before or just after). The PM will conduct a detailed psychosocial and needs assessment with each willing CG and assess the patient based on both a standardized assessment and clinical judgement. The PM will also engage those CGs who live far from the patient and who manage the patient remotely through paid home health aids (HHA). The CG psychosocial assessment will focus on diabetic management support and family dementia CG support providing referrals as needed to well established New York City programs. The PM will provide PCPs with evaluation data, DM-relevant care suggestions and facilitate PCP visits for care reassessment as clinically appropriate. The PM will assist the PCP and the dyad with developing individualized DM management targets and re-evaluating these targets over time. The PM will maintain dyad follow-ups and monitor patient-level data using EHR follow-up data as per usual clinical care, and an Epic-generated report for relevant issues. The PM will also address dyad goals and treatment preferences and assist with communicating these with the PCP. A key part of PM activity will be determining with each PCP their preferred method of communication (e.g., Epic messaging, order pending, periodic phone calls, etc).

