### **CON Clinics:**

Providers will get a list of eligible patients DM-ADRD initially, giving them the opportunity to follow the decisional guidance. In addition, the guideline will specify cognitive screening in DM patients,  $\geq 75$  years with high or low HbA1cs or BP's because we suspect that these values may represent self-management red flags due to cognitive (especially memory and executive) impairment. During training the CON providers will be encouraged to do cognitive screening as well as follow the guidelines in general. Clinics can decide who does the cognitive screen, such as a RN or MA, using the MiniCog™ we will address this issue in the guideline and during provider training. Per guidelines, any patient with a MiniCogTM score  $< 3$  of 5 should have further cognitive assessment per the guideline and preferences of the patient/caregiver dyad. These patients will also become eligible for the evaluation and can be identified by periodic research staff EHR identification of patients with DM-ADRD diagnoses in the CON clinics. When identified we will enroll them for the evaluation (4.2). As with INT clinic patients, we anticipate patient/caregiver loss over the 3 years of the study and the sample will be refreshed with patients with new diagnoses and who are new to the clinic. The investigators will visit CON clinics yearly to discuss care of patients with DM-ADRD. These meetings will serve to answer questions, get feedback from PCPs and provide general feedback on the progress of the quality improvement program.

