## 7. Data Analysis

We will begin all analyses with descriptive summary statistics and graphical displays of all variables. Continuous variables will be summarized with means, medians, standard deviation and interquartile range; categorical variables will be summarized with frequencies. We will assess the balance by treatment assignment of patients in the INT and CON clinics with respect to demographic and clinical characteristics (e.g., age, gender, Charlson Index, socioeconomic status, baseline TBQ, etc.) using standard tests (t-tests, Wilcoxon rank-sum tests, and  $\chi^2$  tests as appropriate). Any factors that appear to be unbalanced by treatment assignment will be considered as adjustment factors in the primary analyses. All hypothesis testing will be two-sided and conducted using a significance level of 0.05.

The primary outcome of 'on target' HbA1C values will be measured for each patient as a binary indicator. The primary analysis will use a generalized linear mixed model approach, with a logit link, for the probability of being 'on target.' The treatment group (CON vs INT) will be the primary fixed effect of interest; we will also include the practice as a random effect to accommodate clustering of patients within clinics. We will also explore non-parametric methods such as quantile regression or other rank-based approaches. As noted above, randomization should obviate the need for any additional covariate adjustment, but we will explore whether adjustment for clinic-level characteristics (e.g., clinic size) and provider-level characteristics (e.g., provider demographics and panel size) is necessary. We will use standard assessments of goodness-of-fit, including residual plots, to evaluate the models. Finally, in addition to reporting the treatment difference in terms of the odds ratio from the logistic regression, we will report absolute risk difference as well.

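### The Table 1 screening measure counts MiniCog only, so intervention patients screened by panel managers with IQ-CODE count as unscreened and screening is understated in the intervention arm alone

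*Combined protocol and SAP*

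**What the plan says.** Section 5.4, Table 1, lists one screening row among the EQUIPED process-of-care measures. It is taken from the EHR at 6, 12 and 24 months and defined as "Proportion (n, %) of DM-eligible patients screened w/ MiniCog". The text after the table lists the measure again as "cognitive screening of diabetes patients over 75", without naming an instrument.

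The instruments are assigned in Section 4:

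- Both arms: "Providers will also be trained in cognitive screening with the MiniCog".
- INT only (PM Activities): the panel manager contacts patients aged 75 or older with over- or under-treated HbA1c or blood pressure "for cognitive screening using IQ-CODE as defined in the Guideline". This is the only mention of IQ-CODE in the document.
- CON: "Clinics can decide who does the cognitive screen, such as a RN or MA, using the MiniCog". CON clinics have no panel manager.

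Specific Aim 1 (Section 1.2) includes the intention to "identify additional patients with cognitive impairment and inappropriate DM management". Section 4 expects, per INT clinic, 20-50 patients with diagnosed DM-ADRD and "about an equal number with DM without ADRD who will screen positive for cognitive impairment".

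**The concern.** The CON screening route falls wholly within the numerator. The INT route has two parts, and only the clinic's MiniCog use is counted. The panel manager's IQ-CODE outreach is something the programme adds in INT, yet under the stated definition it contributes nothing to the programme's own screening measure.

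The error runs in one direction. It lowers the INT value, leaves CON untouched, and grows with the number of patients the panel managers reach. A reader of the implementation results could conclude that the programme did little for cognitive screening when it did a good deal. What is at stake is the fidelity and implementation account and, by inference, what the trial can say about the case-finding part of Aim 1.

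**Working it through.** The plan states no screening rate, sample size or power for this measure, so there is no figure to reproduce. The check is an identity, evaluated over assumed rates.

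**Inputs**

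- From the documents: the numerator is MiniCog only (Table 1); IQ-CODE is used by panel managers in INT only (Section 4, PM Activities); MiniCog is available in both arms (Section 4).
- Assumed, because the documents give none: c = proportion of CON patients screened with MiniCog, 10-40%; m = proportion of INT patients screened with MiniCog, from 0 up to c, plus cases above c; q = proportion of the remaining INT patients screened with IQ-CODE, 30-70%.

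**Formulas**

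- Difference on the Table 1 definition: m - c
- Difference counting either instrument: [m + (1 - m)q] - c
- Shortfall of the Table 1 difference: (1 - m)q, which is never negative and does not depend on c
- The sign reverses only when m < c < m + (1 - m)q

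**Worked cases with c = 20% and q = 50%**

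| m | INT, either instrument | Table 1 difference | Either-instrument difference | Shortfall |
|---|---|---|---|---|
| 10% | 10 + 0.5 × 90 = 55% | 10 - 20 = -10 | 55 - 20 = +35 | 45 points |
| 20% | 20 + 0.5 × 80 = 60% | 20 - 20 = 0 | 60 - 20 = +40 | 40 points |
| 30% | 30 + 0.5 × 70 = 65% | 30 - 20 = +10 | 65 - 20 = +45 | 35 points |

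The three rows are a reversal, a hidden effect, and a shrunken effect that keeps its sign.

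**Grid of 60 scenarios** (c = 10, 20, 30, 40%; m = 100, 75, 50, 25, 0% of c; q = 30, 50, 70%)

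- m = c (12 scenarios): the Table 1 difference is exactly 0. The either-instrument difference is (1 - c)q, from 0.6 × 30 = +18 to 0.9 × 70 = +63 points.
- m < c (48 scenarios): 45 reverse sign. In the other 3 (c = 30%, m = 0, q = 30%; c = 40%, m = 10% or 0, q = 30%) INT has no real advantage to reverse.
- m > c lies outside the grid. By the formulas, the gain is understated and the sign is kept.

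The count of 45 describes the grid that was chosen; it is not a probability of reversal.

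**Denominator.** Three populations are in play: DM-eligible patients (Table 1), diabetes patients over 75 (text after the table), and patients aged 75 or older with out-of-range HbA1c or blood pressure (Section 4, both arms). IQ-CODE outreach covers only the last. If that group is a fraction f of the denominator and no one else is contacted, the shortfall is f(1 - m)q, with m and q taken within the group. A broader denominator shrinks the bias but does not remove it.

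**Scale.** Section 4 implies roughly 9 × 20 = 180 to 9 × 50 = 450 screen-positive patients without an ADRD diagnosis across the 9 INT clinics. More than that must be screened to find them. The documents do not say how many would be screened by IQ-CODE.

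**The case against.** The strongest reply is that this is one table cell set against instrument-neutral wording elsewhere. The text after Table 1 names no instrument, and the INT provider feedback described in Section 4 counts older adults with diabetes who were screened, by whatever means. That is a fair reason to call this an inconsistency to reconcile. It does not settle the matter, because neither place brings IQ-CODE into the Table 1 numerator; the measure is left with two possible definitions.

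Four stronger readings are tempting, and the documents do not support them.

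- *The arm comparison is expected to reverse.* Reversal needs INT MiniCog use to fall below CON. The idea that clinic staff would skip MiniCog once a panel manager has screened appears nowhere in the plan. Some features point the other way: only INT providers receive monthly lists that include patients aged 75 or older who are out of range, while CON providers receive an initial list of DM-ADRD patients.
- *INT screening is left out altogether.* INT providers are trained in MiniCog, and their screens count.
- *Aim 1 will be answered wrongly.* Table 1 ties the row to no aim. Aim 1 speaks of patients identified, which is yield rather than screening rate, and dementia diagnosis is collected separately at baseline and 24 months. The link to Aim 1 is an inference.
- *A planned test is biased.* Section 7 sets a general rule, "All hypothesis testing will be two-sided and conducted using a significance level of 0.05", but specifies no model or contrast for any process measure.

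It is also true that the consensus guideline, to which the protocol defers on screening, is not part of the documents and may say how the two instruments are sequenced and recorded. That limits what can be said about the size of the effect. It does not change what the Table 1 row counts.

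**Conclusion.** The mismatch stands on the current text. Any INT patient screened only with IQ-CODE is counted as unscreened, and CON has no counterpart, so the process measure understates screening in INT alone, by (1 - m)q of the group reached. A real INT advantage is shrunk if INT MiniCog use exceeds CON and hidden if the two are equal. It could reverse only if INT MiniCog use is lower.

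The direction needs no assumed rate, only that some INT patients are screened by IQ-CODE alone. The size rests entirely on assumed rates and on which denominator applies. The HbA1c primary outcome and the secondary outcomes (treatment burden, dementia symptoms, utilization) are not touched. The point merits correction because the bias is one-sided and cheap to remove, not because it threatens the main result.

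**What to change.** 1. Redefine the Table 1 row as the proportion of eligible patients with any documented cognitive screen, MiniCog or IQ-CODE. Use the same numerator in both arms and report it by instrument and by who performed it (panel manager or clinic staff).
2. Set one denominator and use it throughout, reconciling the three populations now named in Table 1, the text after it, and Section 4.
3. Confirm that panel-manager IQ-CODE results are recorded in Epic in a form that can be extracted.
4. Align the INT feedback metric with this definition. It already names no instrument, so it needs only to match.

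This concerns what is counted; it takes no position on which instrument either arm should use.

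The cost is a wording change and one added data element from a source already in use. There are two small downsides. Instruments with different properties share a numerator, which the breakdown makes visible. Reading panel-manager records can also reveal the arm to the coordinator whom Section 5.4 describes as blinded. The existing rows on panel-manager contacts and communication already carry that risk, and an administrative Epic extract is preferable to manual chart review for this reason.
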